### 3. OVERALL STUDY DESIGN AND PLAN DESCRIPTION

#### 3.1. STUDY DESIGN

*The following paragraph [protocol, page 20] has been changed from:*

Recruitment will be competitive among the study sites, until the planned number of patients is enrolled. Competitive recruitment has been chosen to increase the speed of recruitment and to account for any difference in transplant rate among study sites. Each centre will enroll patients as rapidly as possible, up to a maximum of 40 patients (as per the randomization list).

*To:*

Recruitment will be competitive among the study sites, until the planned number of patients is enrolled. Competitive recruitment has been chosen to increase the speed of recruitment and to account for any difference in transplant rate among study sites. Each centre will enroll patients as rapidly as possible, up to a maximum of 40 patients (as per the randomization list). A maximum of 48 patients is allowed for the site of the Primary Investigator.

**Reason:** The study design has been changed considering current patient enrollment status. Specifically, since the first patient randomized to the trial back in February 2014, recruitment is extending considerably longer than originally expected. To date, 86 patients have received TP-IAT, out of 89 randomized. New sites in addition to those originally involved have joined the trial with Cincinnati and UCSF having been initiated early in 2016. Despite this continuous effort, overall enrollment rate across the 9 participating sites is lower than predicted, mainly due to the very rare condition of the TP-IAT procedure, coupled with a non-homogeneous distribution of this procedure across the US states/sites. In particular, enrollment rate has significantly decrease since the site of the Primary Investigator (UMN) has reached the cap of 40 patients (out of 89 randomized to date) allowed at a single site as per protocol. The high enrollment rate of this site actually reflects the high volume of TP-IAT procedures specific for Minnesota. Therefore, considering the importance of:

- maintaining study continuity;
- achieving a timely completion of the trial in order to avoid “dilution” over time of data obtained and potential bias on data reproducibility;
- distribution of TP-IAT procedures across different US sites;

the study design has been changed to allow enrollment at the site of the Primary Investigator up to a total of 48 patients.

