### **3. OVERALL STUDY DESIGN AND PLAN DESCRIPTION**

#### **3.1. STUDY DESIGN**

The study will be a phase 2/3, multicenter (US), randomized, double-blind, placebo-controlled, parallel assignment pilot study.

The goal of this study is to reach a total of 100 adult patients who are randomized and receive IAT after total or completion pancreatectomy. Patients will be randomly (1:1) assigned to receive either reparixin [continuous i.v. infusion for 7 days (168hrs)], or matched placebo (control group), starting approximately 12hrs before islet infusion. The two groups will be balanced within each centre. All patients who are randomized and receive the Investigational Product (either reparixin or placebo) will be included in the ITT analysis. Patients will be in the ITT analysis whether or not they receive IAT, because exclusions cannot be made for events occurring after randomization that could be influenced by the randomized assignment.

Recruitment will be competitive among the study sites, until the planned number of patients is enrolled. Competitive recruitment has been chosen to increase the speed of recruitment and to account for any difference in transplant rate among study sites. Each centre will enroll patients as rapidly as possible, up to a maximum of 40 patients (as per the randomization list). A maximum of 48 patients is allowed for the site of the Primary Investigator. Each patient will be involved in the study for 7 day hospital stay during pancreatectomy followed by islet transplantation, for all required measurements up to hospital discharge and for 2 post-transplant visits scheduled @ day  $75\pm 14$  and  $365\pm 14$  after the transplant.

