#### Primary Analysis

The proportion of insulin-independent patients will be compared between treatment groups using the Cochran-Mantel-Haenszel test stratified by baseline IEQ/kg (<2500 IEQ/kg, 2500-5000 IEQ/kg, and >5000 IEQ/kg). The hypothesis to be tested is:

Null Hypothesis,  $H_0$ :  $p_{\text{reparixin}} \leq p_{\text{placebo}}$  for all baseline IEQ/kg strata

Alternative Hypothesis,  $H_A$ :  $p_{\text{reparixin}} > p_{\text{placebo}}$  for at least one baseline IEQ/kg strata

The significance level used for statistical testing will be 2.5% and a one-sided test will be used. The 95% confidence interval for treatment proportions and the one-sided 95% confidence interval for the difference in treatment proportion between reparixin and placebo will be produced.

As a sensitivity analysis, the primary analysis will be repeated for the ITT population, dropping from the analysis any site with >20% of subjects not having data for the primary endpoint recorded; subjects will be considered to not have data recorded for the primary endpoint if they have discontinued the study prior to attending the Day 365 visit or if they have attended the Day 365 visit but did not have the primary endpoint recorded. The intent is to examine the sensitivity of the primary analysis to sites lacking a reasonable number of patients with data captured for the primary endpoint.

The relevance of the treatment-by-site interaction will be investigated using a logistic regression model which will include the main effect of treatment and IEQ/kg infused at IAT (<2500 IEQ/kg,

REP0112

Statistical Analysis Plan

2500-5000 IEQ/kg, and >5000 IEQ/kg) and site as covariates. The analysis variable for treatment will be coded such that the reference treatment is placebo, the analysis variables for IEQ/kg infused at IAT will be coded such that the reference group is <2500 IEQ/kg, and the analysis variables for site will be coded such that the reference site is Site 1. The treatment-by-site interaction will be examined, and if not significant at the 0.10  $\alpha$ -level, will be removed from the model. The hypothesis to be examined is:

Null Hypothesis,  $H_0$ :  $\beta_{\text{treatment}} \leq 0$

Alternative Hypothesis,  $H_A$ :  $\beta_{\text{treatment}} > 0$

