The treatment effect ( $\beta_{\text{treatment}}$ ) will be declared significantly greater than 0 at the 0.025  $\alpha$ -level. A model parameter estimate and the corresponding standard error, p-value, and odds ratio with a one-sided 95% confidence interval will be presented for the treatment effect.

The logistic regression sensitivity analysis will also be performed for the ITT population, dropping from the analysis any site with >20% of subjects not having the primary endpoint recorded, using the same approach used for the sensitivity analysis of the primary endpoint.

As further sensitivity analysis, the primary endpoint analysis and the corresponding logistic regression analysis will be repeated including Site 01 only, which is the largest site with the greatest number of patients receiving IAT, having possibly the best treatment balance, having a high rate of primary endpoint data capture, and also being the site with the highest experience in the field and thus transplanting patients under highly reproducible surgical and clinical conditions. When performing the logistic regression analysis, site will no longer be considered a covariate in the model. The intent of these analyses is to examine the sensitivity of the primary analysis to the low enrollment/treatment balance, lesser experience level, and lower rates of retention which may be present at the other sites.

For both the primary and sensitivity analyses, patients who die or who discontinue before the primary endpoint assessment at Day 365  $\pm$  14 days after IAT, or those who reach the Day 365 visit but have no primary endpoint assessment, will be treated as primary endpoint failures.

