## 7.5.2 Secondary Variables

### 7.5.2.1 Area Under the Curve for C-peptide During First 4 Hours of a Mixed Meal Tolerance Test

C-peptide is to be collected at 9 time points (2 basal measurements and at 15, 30, 60, 90, 120, 180, and 240 minutes) during the first 4 hours of a mixed meal tolerance test on both Days 75 and 365 after IAT. For both Days 75 and 365, the area under the curve normalized by IEQ/kg infused during IAT will be computed as described in Section 5 of this SAP. AUC values at each day will be summarized descriptively by treatment group.

Analysis will be performed in two steps. First, the AUC normalized by IEQ/kg infused during IAT at each day will be compared between treatment groups using the t-test (two-sided tests at the 5% level of significance).

Second, the AUC normalized by IEQ/kg infused during IAT at the two days will be analyzed by a repeated measurements model using PROC MIXED within SAS®. The model will include fixed effect terms for site, time (Days 75 and 365), and treatment. Time will be specified as a repeated measurement. In order to select an appropriate matrix for the observations within each patient, 3 models will be fitted using the compound symmetry, Huynh-Feldt, and unstructured covariance structures. The matrix for the final model will be selected using Akaike's Information Criterion where the lowest value indicates the best fit. Type III sums of squares from the mixed procedure within SAS® will be used to assess the significance of individual terms within the model using the selected matrix structure. The importance of the treatment-by-site interaction will be investigated and if the term is not significant at the 0.10  $\alpha$ -level, it will be excluded from the model. A logarithmic transformation of the data will be considered if found to be more suitable.

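### If the treatment-by-site interaction survives its 0.10 screen, the logistic sensitivity analysis reports the Site 1 effect as the treatment effect, and the SAP names neither the screening test nor a fallback

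*SAP*

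**What the plan says.** SAP 7.5.1 fits a logistic model with treatment, IEQ/kg group and site, and specifies that "the analysis variables for site will be coded such that the reference site is Site 1". On the interaction it says "The treatment-by-site interaction will be examined, and if not significant at the 0.10" level, it leaves the model; by implication it otherwise stays. The treatment coefficient "will be declared significantly greater than 0 at the 0.025" level, and one result is tabulated: "odds ratio with a one-sided 95% confidence interval will be presented for the treatment effect". The text available for review does not say what is reported when the interaction is kept. It also does not name the test used for the screen, and gives no pooling rule or penalised or exact method for sparse sites.

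On site sizes, the amendment rationale for Protocol 3.1 says "overall enrollment rate across the 9 participating sites is lower than predicted" and that the Primary Investigator's site "has reached the cap of 40 patients (out of 89 randomized to date) allowed at a single site as per protocol". Current Protocol 3.1 adds: "A maximum of 48 patients is allowed for the site of the Primary Investigator". SAP 7.5.1 calls Site 01 the largest site and foresees low enrolment and poorer treatment balance elsewhere.

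The mixed models use the same screen. SAP 7.5.2.1, for example, says "The importance of the treatment-by-site interaction will be investigated and if the term is not significant at the 0.10" level, it is excluded.

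**The concern.** Two models sit behind one reported number. Without the interaction, the treatment coefficient is a site-adjusted effect across the trial. With it, under reference coding, the coefficient is the effect at Site 1 only. The data choose between these two estimands through a screen run on very small site-by-arm cells, and the SAP does not define the test. A supportive analysis could then seem to contradict, or seem to confirm, the primary result only because the model switched and about half the patients stopped contributing to the coefficient.

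**Working it through.** **Inputs.** SAP 3.3 gives insulin-independence rates of 13%, 23% and 55% on placebo and 40%, 55% and 84% on reparixin in the three IEQ/kg strata, and a recent stratum mix of 34/42/24%. SAP 3.4 gives blocks of 4 within centre. SAP 3.3 plans 100 transplanted patients plus about 5 others. The amendment rationale gives nine sites; the largest has 40 to 48 patients and is taken to be Site 01. Sizes of the other sites are not in the documents and are assumed.

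**1. The plan's own power figure.** For 23% vs 55% with 44 per arm, SE = √[(0.23×0.77 + 0.55×0.45)/44] = 0.098. Then 0.32/0.098 − 1.96 ≈ 1.30, which gives 90.3% power. Exact binomial power is 88.8%. Both agree with the stated 90% and the 87% to 90% range.

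**2. What the coefficient means.** Take successes on reparixin vs placebo of 12/24 vs 6/24 at Site 1, 2/10 vs 6/10 at site 2 and 5/10 vs 3/10 at site 3, leaving out the IEQ/kg term. With the interaction in the model and Site 1 as reference, the reported odds ratio is (12/12)/(6/18) = 3.00. With site 2 as reference it is (2/8)/(6/4) = 0.17, and with site 3 it is (5/5)/(3/7) = 2.33. The main-effects model gives 1.47.

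**3. Sparse cells.** The other eight sites average between (100−48)/8 = 6.5 and (105−40)/8 = 8.1 patients, or about 3 to 4 per arm. Overall rates are:
- placebo: 0.34×0.13 + 0.42×0.23 + 0.24×0.55 = 27.3%
- reparixin: 0.34×0.40 + 0.42×0.55 + 0.24×0.84 = 56.9%

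A cell of n patients with rate p has all-equal outcomes with probability pⁿ + (1−p)ⁿ. That is 0.405 (n = 3) or 0.285 (n = 4) on placebo and 0.264 (n = 3) on reparixin. For Site 1 = 48 and the others 6,6,6,6,7,7,7,7:
- expected number of such cells: 4×0.405 + 4×0.285 + 8×0.264 ≈ 4.9 of 18
- probability of none: 0.595⁴ × 0.715⁴ × 0.736⁸ ≈ 0.003

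So at least one occurs in 99.7% of trials. For Site 1 = 40 the figure is 98.9% (N = 100) or 97.7% (N = 105), and for uneven sites it is essentially 100%. Even at 50% success in both arms, with Site 1 = 40 and N = 105, it is 87%. Each such cell leaves an interaction coefficient without a finite estimate.

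**4. The screen.** 1,000 simulated trials per layout, planning rates, no treatment-by-site interaction built in, one-sided 0.025 test:

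| Assumed sizes (Site 1 first) | Separated or empty cell | Empty cell | Kept, LR | Kept, Wald | Power, main effects | Power, Site 1 coefficient |
|---|---|---|---|---|---|---|
| 48; 6,6,6,6,7,7,7,7 | 99.8% | 0% | 27.3% | 0.0% | 91.2% | 60.9% |
| 40; 8,8,8,8,7,7,7,7 | 98.9% | 0% | 28.6% | 0.1% | 91.3% | 54.0% |
| 48; 16,12,8,7,5,4,3,2 | 100% | 35.8% | 18.3% | 0.1% | 91.4% | 61.6% |

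With both arms at placebo rates, the likelihood-ratio (LR) screen keeps the term in 20.5%, 24.1% and 17.4%. The main-effects coefficient alone then rejects in 1.9% to 2.6% of trials and the Site 1 coefficient alone in 2.0% to 2.4%, so neither inflates type I error taken alone.

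**5. The rule as written.** With sizes 48,12,10,8,7,6,4,3,2, the LR screen keeps the term in 22% of trials. In those, the Site 1 coefficient is significant in 56% and the main-effects coefficient in 89%. Power is therefore about 0.91 − 0.22×(0.89 − 0.56) = 0.84. A repeat run counted directly gave 23.5% kept and a fall from 90.7% to 82.7%. With a Wald screen that run kept none, and power stayed at 90.7%.

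**6. Mixed models.** Separation has no counterpart for continuous outcomes; only empty cells matter. Under blocks of 4, a randomized site-by-arm cell can be empty only at a site with two or fewer patients. With two patients, the chance that both are in one arm is 2×(1/6) = 1/3.

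**The case against.** The strongest reply is that the damage depends on a test the SAP does not name. Under a Wald screen the standard errors at separated sites become so large that the term is almost never kept. The rule then amounts to the main-effects model. This stands: the 17% to 29% retention and the power loss belong to a likelihood-ratio screen and should not be quoted without that condition. It does not rescue the plan, because a nominal 10% test that rejects in 0% to 0.3% of trials is a poor instrument for investigating heterogeneity. The simulations covered only the case of no true interaction, so its sensitivity to a real one was not measured.

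A reader might also infer that the analysis as a whole cannot be estimated. The documents do not support that. Infinite estimates concern the small sites; the Site 1 coefficient, which is what would be reported, rests on about 24 patients per arm and was well behaved in 99.7% of simulated trials. Its lower power mostly reflects the use of 48 patients instead of 100.

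Finally, this is a sensitivity analysis, and a Site 01-only analysis is already planned and labelled as such. That limits the consequence.

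**Conclusion.** The point holds as a gap in SAP 7.5.1 that should be closed. The change of meaning is exact algebra and needs no assumption: once the interaction is kept, the reported coefficient, p-value and odds ratio are for Site 1, given IEQ/kg group. The near-certain lack of finite estimates at small sites (about 98% to 100%) rests on the planning rates, nine sites as counted at the amendment, and assumed sizes for eight of them. The fall in power from about 91% to about 82% to 84% rests on these and on a likelihood-ratio screen.

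Two stronger readings should be avoided. The primary conclusion is not at risk, since the Cochran-Mantel-Haenszel test is stratified by IEQ/kg only. Nor can failure of the least squares means be presumed in the mixed models: it needs both a retained interaction and a site with very few evaluable patients, and empty cells did not occur in the even layouts. Missing visits could add some, but the documents give no basis for a figure. The retention rates above also cannot be carried over to the Type III tests used there.

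The addendum's Section 3.2.1 on the primary variable is not in the text available for review, so whether it alters this model could not be checked.

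**What to change.** In SAP 7.5.1, state that the treatment effect is always taken from the main-effects logistic model (treatment, IEQ/kg group, site) and that the interaction test never selects the reported model. Present heterogeneity descriptively, for example as treatment by Site 01 versus all other sites, and name the test used. Pooling small sites in the main-effects model is optional; the model with all sites already has about 91% power.

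In the mixed models, likewise report the treatment difference from the model without treatment-by-site.

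The cost is a change of SAP wording, plus the loss of effect estimates at individual small sites, which cells of 3 to 4 patients could not supply reliably.

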## 7.5.2 Secondary Variables

### 7.5.2.1 Area Under the Curve for C-peptide During First 4 Hours of a Mixed Meal Tolerance Test

C-peptide is to be collected at 9 time points (2 basal measurements and at 15, 30, 60, 90, 120, 180, and 240 minutes) during the first 4 hours of a mixed meal tolerance test on both Days 75 and 365 after IAT. For both Days 75 and 365, the area under the curve normalized by IEQ/kg infused during IAT will be computed as described in Section 5 of this SAP. AUC values at each day will be summarized descriptively by treatment group.

Analysis will be performed in two steps. First, the AUC normalized by IEQ/kg infused during IAT at each day will be compared between treatment groups using the t-test (two-sided tests at the 5% level of significance).

Second, the AUC normalized by IEQ/kg infused during IAT at the two days will be analyzed by a repeated measurements model using PROC MIXED within SAS®. The model will include fixed effect terms for site, time (Days 75 and 365), and treatment. Time will be specified as a repeated measurement. In order to select an appropriate matrix for the observations within each patient, 3 models will be fitted using the compound symmetry, Huynh-Feldt, and unstructured covariance structures. The matrix for the final model will be selected using Akaike's Information Criterion where the lowest value indicates the best fit. Type III sums of squares from the mixed procedure within SAS® will be used to assess the significance of individual terms within the model using the selected matrix structure. The importance of the treatment-by-site interaction will be investigated and if the term is not significant at the 0.10  $\alpha$ -level, it will be excluded from the model. A logarithmic transformation of the data will be considered if found to be more suitable.

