##### **9.4.2. Primary and Secondary Endpoint analysis**

For the primary efficacy endpoint, the proportion of insulin-independent patients over the time frame of day 365 $\pm$ 14 after the transplant, the differences in proportions will be assessed using the Pearson Chi-square statistic, stratified by the three groups at baseline: < 2500 IEQ/kg vs. 2500-5000 IEQ/kg vs. > 5000 IEQ/kg. The significance level used for statistical testing will be 2.5% and one-sided test will be used. The 95% confidence interval for treatment proportions and for the difference in treatment proportion between reparixin and placebo will be produced. The primary analysis will be performed using both ITT population with PP analysis serving as a sensitivity analysis.

For secondary endpoints that will be tested both at 75 $\pm$ 14 and 365 $\pm$ 14 days after the transplant, only the day 365 $\pm$ 14 time point will be tested for superiority in the fixed sequence testing procedure.

The C-peptide AUC after the MMTT normalized by IEQ/kg will be analyzed at the two time points by a repeated measurements model using PROC MIXED within SAS®, including terms for treatment, time point and center. The treatment effect within each time point will be compared using a two-sided test at the 5% level. The estimated treatment difference between reparixin and placebo at each time point will be presented together with the corresponding 95% confidence interval. The confidence interval will be generated using  $\alpha=0.05$ .

The mean in average daily insulin requirements at the two time points will be analyzed using a repeated measurements model using PROC MIXED within SAS®. The model will include fixed effect

terms for center, time point and treatment. Time point will be specified as a repeated measurement. The treatment effect within each time point will be compared using a two sided test at the 5% level.

The proportion of patients with an HbA1c  $\leq 6.5\%$  will be analyzed at day  $365 \pm 14$ . Additionally, the proportion of patients with an HbA1c  $\leq 6.5\%$  at day  $365 \pm 14$  will be analyzed again, but patients are included in this second analysis if they are also free of severe hypoglycemic events from day  $75 \pm 14$  to day  $365 \pm 14$  inclusive. Treatment effect will be analyzed using Pearson Chi-square.

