### 1.2 Changes From Protocol

Not pertinent.

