## 7.3 Methods for Multiplicity Correction in Analyses

If the primary analysis of the primary endpoint leads to rejection of the null hypothesis, the null hypotheses for the following secondary endpoints will be tested in a conditional sequential manner. The sequence in which these secondary endpoints will be tested is as follows:

1. AUC for serum C-peptide level during the first 4 hours of a MMTT, normalized by the number of IEQ/kg, at Day 365 ± 14 days after IAT.
2. Average daily insulin requirement at Day 365 ± 14 days after IAT.
3. Time course of C-peptide derived from the MMTT at Day 365 ± 14 days after IAT.
4. β-cell function as assessed by β-score at Day 365 ± 14 days after IAT.
5. The proportion of patients with HbA1c ≤ 6.5% at Day 365 ± 14 days after IAT.

REP0112

Statistical Analysis Plan

6. Cumulative number of severe hypoglycemic events from Day 75 ± 14 days to Day 365 ± 14 days after IAT.
7. The proportion of patients with HbA1c ≤ 6.5% at Day 365 ± 14 days after IAT **AND** free of severe hypoglycemic events from Day 75 ± 14 days to Day 365 ± 14 days after IAT, inclusive.

A null hypothesis will be rejected if and only if the primary analysis of that endpoint and all primary analyses of preceding primary and secondary endpoints result in a rejection of the respective null hypotheses. This procedure protects the family-wise false positive error rate at the overall one-sided 0.025 level.

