#### 7.5.2.2 Average Daily Insulin Requirements

The average daily insulin requirement (ADIR) will be computed by site personnel using data from the patient diary card and reported on Pages 24 and 24.1 for Days 75 and 365, respectively. ADIR values at each day will be summarized descriptively by treatment group.

ADIR will be analyzed in two steps as done for AUC of C-peptide. First, ADIR at each day will be compared between treatment groups using the t-test (two-sided tests at the 5% level of significance). Second, ADIR at Day 75 and Day 365 will be analyzed as repeated measures with a single repeated measurements model using PROC MIXED within SAS®. The model will include fixed effect terms for site, time (Days 75 and 365), and treatment. Time will be specified as a repeated measurement. In order to select an appropriate matrix for the observations within each patient, 3 models will be fitted using the compound symmetry, Huynh-Feldt, and unstructured covariance structures. The matrix for the final model will be selected using Akaike's Information Criterion where the lowest value indicates the best fit. Type III sums of squares from the mixed procedure within SAS® will be used to assess the significance of individual terms within the model using the selected matrix structure. The importance of the treatment-by-site interaction will be investigated and if the term is not significant at the 0.10  $\alpha$ -level, it will be excluded from the model. A logarithmic transformation of the data will be considered if found to be more suitable.

The adjusted least squares means and associated 95% confidence intervals will be estimated for each combination of day and treatment, and the adjusted least squares mean difference (reparixin minus placebo) and associated 95% confidence interval at each day will also be estimated. The treatment effect within each day will be tested using a two-sided test at the 5% level. The tests of the fixed effects in the model will also be presented.

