#### 7.5.2.3 Time Course of Glucose, C-peptide, and Insulin

Glucose, C-peptide, and insulin are to be collected at 9 time points (2 basal measurements and at 15, 30, 60, 90, 120, 180, and 240 minutes) during the first 4 hours of a mixed meal tolerance test on both Days 75 and 365 after IAT.

The time course of each of these parameters at Days 75 and 365 will be analyzed separately with a repeated measurements model using PROC MIXED within SAS®. Each repeated measures model will include fixed effect terms for site, time (the average of 2 basal measurements at time 0 and at 15, 30, 60, 90, 120, 180, and 240 minutes), and treatment. Time will be specified as a repeated measurement. In order to select an appropriate matrix for the observations within each patient, 3 models will be fitted using the compound symmetry, Huynh-Feldt, and unstructured covariance structures. The matrix for the final model will be selected using Akaike's Information Criterion where the lowest value indicates the best fit. Type III sums of squares from the mixed procedure within SAS® will be used to assess the significance of individual terms within the model using the selected matrix structure. The importance of the treatment-by-site interaction will be investigated and if the term is not significant at the 0.10  $\alpha$ -level, it will be excluded from the model. A logarithmic transformation of the data will be considered if found to be more suitable.

Separately for each day (Day 75 and Day 365), parameter values at each time point will be summarized descriptively by treatment group. The adjusted least squares means and associated 95% confidence intervals will be estimated for each combination of time and treatment, and the adjusted least squares mean difference (reparixin minus placebo) and associated 95% confidence interval at each time will also be estimated. The treatment effect within each time will be tested using a two-sided test at the 5% level. Adjusted least squares means for each treatment and the treatment effect, associated 95% confidence intervals, and a two-sided p-value testing treatment effect over all time points at the 5% level will also be presented. The tests of

REP0112

Statistical Analysis Plan

the fixed effects in the model will also be presented. The time course of adjusted least squares means for each parameter will be plotted over time.

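### The SAP's rule for the secondary endpoints needs one primary test per endpoint, but the first three endpoints have several 5% tests with none named primary, and the AUC and daily insulin models as written cannot give the Day 365 effect

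*SAP*

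**What the plan says.** - **The rule.** Under SAP 7.3 a hypothesis is "rejected if and only if the primary analysis of that endpoint and all primary analyses of preceding primary and secondary endpoints" lead to rejection. The section adds: "This procedure protects the family-wise false positive error rate at the overall one-sided 0.025 level". Protocol 9.4.7 makes the same claim. Steps 1 to 3 are normalized C-peptide AUC, average daily insulin and the C-peptide time course, all at Day 365.
- **AUC (SAP 7.5.2.1).** "Analysis will be performed in two steps. First, the AUC normalized by IEQ/kg infused during IAT at each day will be compared" by t-test at two-sided 5%. A repeated-measures model with site, time and treatment follows. It is to give a treatment difference on each day, tested at two-sided 5%, and tests of the fixed effects are also presented. A log transformation may be used if judged more suitable.
- **Daily insulin (SAP 7.5.2.2).** Same structure: "First, ADIR at each day will be compared between treatment groups using the t-test", then the mixed model.
- **C-peptide time course (SAP 7.5.2.3).** A test at each of eight times (averaged basal plus seven post-meal samples), and "a two-sided p-value testing treatment effect over all time points at the 5% level will also be presented".
- **Protocol 9.4.2.** One method for AUC: "The C-peptide AUC after the MMTT normalized by IEQ/kg will be analyzed at the two time points by a repeated measurements model". Daily insulin is handled the same way. Neither has a t-test, and no specific test is given for the time course.
- **SAP 1.2 (Changes From Protocol).** "Not pertinent".
- **SAP Addendum 3.1.** The SAP's efficacy endpoints will be interpreted without the sequential correction.

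**The concern.** A fixed sequence controls error only if each step has one pre-specified p-value. Here steps 1 to 3 have between two and nine, and nothing ranks them. SAP 7.5 attaches the word primary only to the ITT population. For the primary variable, SAP 7.5.1 does separate a primary analysis from sensitivity analyses; the secondaries have no such separation.

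The listed tests are also not interchangeable. The t-test uses Day 365 alone. A mixed model with treatment and time but no treatment-by-time term estimates one treatment effect shared by Day 75 and Day 365, so it cannot deliver the day-specific differences that the same section promises. At stake are the error rate stated for the sequence and, if the sequence is dropped, which answer is reported for the key secondary endpoint.

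**Working it through.** **1. The plan's own figure.** SAP 3.3 gives 52 per arm, difference 1.48, SD 1.37 and two-sided alpha 0.0025, with power above 95%.

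- The SD is the pooled pilot value: √[(5×1.62² + 2×0.04²)/7] = 1.369.
- SE = 1.37×√(2/52) = 0.2687, and 1.48/0.2687 = 5.508.
- Power = Φ(5.508 − 3.023) = 0.9935, so the claim reproduces. At two-sided 0.05, the level used in SAP 7.5.2.1, power is Φ(5.508 − 1.960) = 0.9998.
- The planned effect is 1.48/1.37 = 1.08 SD.

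**2. Which model terms are written where.**

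| Place | Treatment-by-time listed? |
|---|---|
| SAP 7.5.2.1 (AUC), 7.5.2.2 (insulin), 7.5.2.3 (time course) | No |
| SAP 7.6.2.2 (AST/ALT), 7.6.3 (weight) | Yes |
| Addendum table shells for un-normalized AUC and for insulin with IEQ/kg | Yes |

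Addendum 3.2.2.1 says the un-normalized AUC follows SAP 7.5.2.1, yet its shell contains the term that SAP 7.5.2.1 omits.

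**3. AUC: chance that at least one listed test favours reparixin when the AUC null is true** (one-sided, nominal 0.025). The correlation ρ between Day 75 and Day 365 is not in the documents, so it is varied.

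- *t-test or pooled treatment term.* With complete data and equal variances, the pooled term tests the mean of the two days. Its correlation with the Day 365 statistic is r = √[(1+ρ)/2], and the rate is 0.05 − Φ₂(−1.96, −1.96; r).
  - ρ = 0.3: r = 0.806, rate 0.05 − 0.0112 = 0.039.
  - ρ = 0.8: r = 0.949, rate 0.05 − 0.0176 = 0.032.
  - Simulation at 50 per arm gives 0.032-0.040.
- *t-test or Day 365 contrast (treatment-by-time included).* Simulation gives 0.026-0.028 without site effects. With 102 patients at nine unequal sites, ρ 0.5-0.7, between-site SD 0-0.6 and 0-15% missing, it gives 0.021-0.030.
- *Both of these plus a pooled term,* in the same site and missing-data setting: 0.033-0.043.

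**4. Time course: any of the eight time-specific tests or the overall test.** With equal correlation between times and a separate effect per time, the rate is 0.126 at correlation 0.5, 0.095 at 0.7 and 0.061 at 0.9. If the model has no treatment-by-time term, the eight tests are the same test and there is no inflation from this source.

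**5. How often the AUC tests disagree when there is an effect.**

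| Effect (Day 75, Day 365) | Tests compared | Trials in which they disagree |
|---|---|---|
| 0.3-0.5 SD, equal on both days, no site effects | t-test, Day 365 contrast | 2-3% |
| 0.3-0.5 SD, equal on both days, no site effects | t-test, pooled term | 10-23% |
| 0.4-0.5 SD, equal on both days, site effects, 10% missing | t-test, Day 365 contrast | 7-11% |
| 0.4-0.5 SD, equal on both days, site effects, 10% missing | all three | 21-26% |
| 0.6, 0.2 SD, site effects, 10% missing | all three | 47-49% |
| 1.08 SD on both days, no site effects | t-test, pooled term | about 0.04% or less |

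The 0.6/0.2 case shows the mechanism: the pooled term estimates (0.6 + 0.2)/2 = 0.4 SD, twice the Day 365 effect. In one skewed-data scenario (0.4 SD, site effects, 10% missing), adding a log-scale model raised disagreement to about 43%.

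**The case against.** The strongest reply has four parts.

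- **Addendum 3.1 switches the sequence off.** This stands. A reader might infer that the choice of AUC test decides whether steps 2 to 7 can be claimed. Under the addendum AUC gates nothing, so that consequence follows only if SAP 7.3 and Protocol 9.4.7 are read without it. Their text has not been changed, so the two need reconciling.
- **The Day 365 contrast is plainly intended.** SAP 7.3 lists the endpoint at Day 365, SAP 7.5.2.1 calls for within-day tests and the addendum shell has the interaction. This is a fair reading, and on it the t-test adds little (0.026-0.028). But the model as written does not produce that contrast, and a pooled treatment test is presented as well.
- **The protocol already supplies one method for AUC and insulin, and SAP 1.2 claims no departure.** That supports treating the t-test as an addition, but the SAP puts it first and never calls it supportive. For the time course the protocol names no specific test. The endpoint's label points to the overall test without saying so.
- **The primary endpoint protects the family.** Under the global null its gate does hold the error at 0.025. A reader might infer general inflation; the documents support it only when the primary has truly succeeded, a secondary null is true and the test is chosen afterwards.

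A reader might also add the AUC and time-course figures together. If the models have no treatment-by-time term, the competing AUC tests are the t-test and the pooled term (0.032-0.040), and the time course shows no inflation. If they have the term, t-test against Day 365 contrast is near nominal and the time course is at 0.06-0.13.

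**Conclusion.** The point holds in a limited form. SAP 7.3 relies on a designation that SAP 7.5.2.1 to 7.5.2.3 never make, and the AUC and insulin models omit the term needed for the effect they are said to test. The excess over one-sided 0.025 is slight for AUC if only the t-test and Day 365 contrast compete, moderate if a pooled term may count, and largest for the time course if effects vary by time.

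These sizes rest on assumed correlations, site variation and missingness, and the disagreement rates also on assumed effects of 0.2-0.6 SD. At the planned 1.08 SD the choice hardly matters. That effect comes from Month 1 data on six treated and three control patients in the islet allo-transplant pilot (Protocol 2.4.2), so smaller effects are plausible. If Addendum 3.1 governs, what remains is two or more competing 5% answers for the key secondary, with no rule for the headline. The change should be made before unblinding; the primary analysis is not affected.

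**What to change.** - In SAP 7.3, 7.5.2.1 and 7.5.2.2, name as primary for normalized AUC and daily insulin the Day 365 treatment difference from the repeated-measures model, with treatment-by-time included and the analysis scale fixed before unblinding. Citing the Protocol 9.4.2 model alone would not be enough, since its terms for these endpoints also omit treatment-by-time.
- In SAP 7.5.2.3, name the overall treatment effect at Day 365 as primary for the C-peptide time course.
- Label the t-tests and time-specific tests supportive, and record the added t-tests under SAP 1.2.
- Reconcile SAP 7.3 and Protocol 9.4.7 with Addendum 3.1. If the sequence stands, only the named p-values enter it; if it does not, they are the headline results.

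The cost is a few lines of text, and every planned analysis is still run. The downside for the sponsor is that it can no longer cite whichever test is more favourable.
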